5.3 LONG-TERM EFFECTIVENESS ANALYSIS SET

Subject who have been administered PRISTIQ® over 6 months out of enrolled patients will be included in the long-term effectiveness analysis set. The long-term effectiveness analysis set is a subset of the effectiveness analysis set.

The following cases are excluded from the long-term effectiveness analysis set:

- Subjects excluded from effectiveness analysis set listed in section 5.2
- Subjects who administrated PRISTIQ® less than 6 months(180 days)
- Subjects whose each drug-free period is more than 14 days
- Subjects who are assessed on the final effectiveness evaluation before 6 months(180 days) treatment of PRISTIQ®

6 ENDPOINTS AND COVARIATES

6.1 SAFETY ENDPOINT(S)

- *Occurrence of Adverse Event*

6.2 EFFECTIVENESS ENDPOINT(S)

- *[Final effectiveness evaluation]*

Final effectiveness will be evaluated at completing the administration of PRISTIQ® or at around 8 weeks treatment if PRISTIQ® has been still administered. In case of long-term use study subject, the result will be assessed after 6 months treatment of PRISTIQ®. Final effectiveness will be evaluated as 'improved', 'no change', 'worse' or 'unevaluable' based on overall patient's clinical response, CGI-I scale and investigator's judgment.

- Improved: In the case of judgment that there is the improvement of symptoms related to MDD.
- No change: In the case that there is no significant change compared to patient's status before PRISTIQ® administration.
- Worse: In the case that symptoms are getting worse compared to patient's status before PRISTIQ® administration.
- Unevaluable: In the case that the medical charts do not have adequate progress notes to make a judgment on clinical response.

- *[CGI-I scale (Clinical Global Impression – Improvement scale)]*

Clinical effectiveness will be evaluated after 8 weeks treatment (within 2 weeks of the last administration) using CGI-I scale as follows. In case of long-term use study subject, the result will be also assessed after 6 months treatment of PRISTIQ® (within 2 weeks of the last administration).

- 1. Very much improved
- 2. Much improved
- 3. Minimally improved
- 4. No change
- 5. Minimally worse
- 6. Much worse
- 7. Very much worse

7 HANDLING OF MISSING VALUES

Not Applicable

8 STATISTICAL METHODOLOGY AND STATISTICAL ANALYSES

8.1 STATISTICAL METHODS

All test statistics will be the results of two-sided tests with the statistical significant level of 0.05.

8.1.1 Analysis for Continuous Data

Descriptive summary statistics for continuous variables will include the following:

- number of subjects (n), mean, standard deviation (SD), median, minimum and maximum.

8.1.2 Analysis for Categorical Data

Descriptive statistics for categorical variables will be given as frequencies and percentages. The denominator will be the number of subjects included either in the safety analysis set or effectiveness analysis set depending on where the analysis is presented. But in case of pregnancy and breast-feeding analysis, subjects who collected “Not Applicable (male)” are excluded from the denominator and footnote will be added to the relevant outputs to indicate the number of subjects collected “Not Applicable (male)”. Likewise, in analysis of severity of disease, subjects who collected “Unknown” are excluded from the denominator and footnote will be added to the relevant outputs to indicate the number of subjects collected “Unknown”.

Where appropriate, the percentages will be presented with a corresponding 95% confidence interval. Comparisons between subcategories of each baseline characteristic will be made using chi-square test or Fisher’s exact test. Test statistics include p-value. When more than 20% of expected frequency of the cell count is less than 5, Fisher’s exact test should be used instead of chi-square test.

8.2 STATISTICAL ANALYSES

8.2.1 Safety Analyses

8.2.1.1 Demographic and Baseline Characteristics

Baseline characteristics for this study are defined as follows:

- Continuous measurements:
 - Age
 - Duration of disease[†]
 - Total administration period of PRISTIQ^{®‡}
 - Total dose of PRISTIQ^{®¶}

- Mean daily dose of PRISTIQ® excluding days of missed doses[§]
- Categorized measurements:
 - Age (< 30 years, \geq 30 years and \leq 49 years, \geq 50 years and \leq 69 years, \geq 70 years^{*})
 - Geriatric status (<65 years, \geq 65 years)
 - Sex (Male, Female)
 - Pregnancy (Yes, No)
 - Breast-feeding (Yes, No)
 - Duration of disease[†] (<3 months, \geq 3 months and <6 months, \geq 6 months^{*})
 - Severity of disease (Mild, Moderate, Severe)
 - Medical History (Past Disease, Present Disease/Yes, No)
 - Allergic history (Yes, No)
 - Recent past psychotropic medication (Yes, No)
 - Total administration period of PRISTIQ^{®‡} (< 4 weeks, \geq 4 weeks and <8 weeks, \geq 8 weeks and <12 weeks, \geq 12 weeks^{*})
 - Mean daily dose of PRISTIQ® excluding days of missed doses (<50 mg/day, \geq 50 mg/day and <100 mg/day, \geq 100 mg/day and \leq 200 mg/day^{*})
 - Renal disorder (Yes, No)
 - Hepatic disorder (Yes, No)
 - Long-term administration (<6 months (180 days), \geq 6 months (180 days) of total administration period of PRISTIQ®)
 - Concomitant medication (Yes, No)

[†] Duration of disease = First start date of PRISTIQ® – Diagnosis Date + 1

Subjects whose diagnosis date is included 'Unknown' are excluded from the analysis
(Footnote will be added to the relevant outputs to indicate the number of subjects collected 'Unknown')

[‡] Total administration period of PRISTIQ® = Sum of each period of administration

- In safety analysis set

Sum of each period of administration = (Last administration end date) – (First administration start date) + 1

If the medication is being continued at the completion of the study, last administration end date is replaced with last date collected in data.
- In effectiveness analysis set
 - If final effectiveness evaluation is evaluated after last administration end date,

Sum of each period of administration = (Last administration end date) – (First administration start date) + 1
 - If final effectiveness evaluation is evaluated before last administration end date or the medication is being continued at the completion of the study,

Sum of each period of administration = (Date of final effectiveness evaluation) – (First administration start date) + 1

[¶] Total dose of PRISTIQ® = Sum of each dose of administration

: Each dose of administration = (Administration end date - Administration start date +1)*(Total daily dose)

§ Mean daily dose of PRISTIQ® excluding days of missed doses = Total dose of PRISTIQ® / Total administration period of PRISTIQ® excluding days of missed doses

* The above categories can be altered depending on the data distribution.

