7.7.2. Effectiveness analysis

Effectiveness endpoints include following variables: CGI-I scale and final effectiveness evaluation result at the date of effectiveness evaluation. Descriptive statistics (cell counts and percents) will be used to summarize this variable within the effectiveness analysis set population; the CGI-I scale and final effectiveness evaluation will also be summarized within subgroups of the effectiveness analysis set formed by demographic and other baseline factors such as sex, age and diagnosis date of MDD, etc. Comparisons across subgroups may be conducted using chi-squared tests at the 0.05 level of significance.

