8.2.1.3 Adverse Events by Baseline Characteristics

The following will be presented for AEs, split by the baseline characteristics using the safety analysis set:

- The number of subjects to whom AE occurred and the number of AEs will be calculated.
- The proportion of subjects to whom AE occurred and its 95% confidence interval will be estimated and compared between subcategories of each baseline characteristic using chi-square test or Fisher's exact test.
- Adverse event presentations will be split by the following baseline characteristics:
 - Age (< 30 years, \geq 30 years and \leq 49 years, \geq 50 years and \leq 69 years, \geq 70 years)
 - Geriatric status (<65 years, \geq 65 years)
 - Sex (Male, Female)
 - Pregnancy (Yes, No)
 - Breast-feeding (Yes, No)
 - Duration of disease (<3 months, \geq 3 months and <6 months, \geq 6 months)
 - Severity of disease (Mild, Moderate, Severe)
 - Medical History (Past Disease, Present Disease/Yes, No)
 - Allergic history (Yes, No)
 - Recent past psychotropic medication (Yes, No)
 - Total administration period of PRISTIQ® (< 4 weeks, \geq 4 weeks and <8 weeks, \geq 8 weeks and <12 weeks, \geq 12 weeks)
 - Mean daily dose of PRISTIQ® excluding days of missed doses (<50 mg/day, \geq 50 mg/day and <100 mg/day, \geq 100 mg/day and \leq 200 mg/day)
 - Renal disorder (Yes, No)
 - Hepatic disorder (Yes, No)

- Long-term administration (<6 months (180 days), \geq 6 months (180 days) of total administration period of PRISTIQ®)
- Concomitant medication (Yes, No)

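### SAP 8.2.1.1 drops subjects with a partly unknown diagnosis date from the disease-duration analysis even when the known year or month already fixes their duration class

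*SAP*

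**What the plan says.** SAP 8.2.1.1 defines the variable as "Duration of disease = First start date of PRISTIQ® – Diagnosis Date + 1", a count in days that needs a complete date. It adds that "Subjects whose diagnosis date is included 'Unknown' are excluded from the analysis", and the only disclosure is a count: "Footnote will be added to the relevant outputs to indicate the number of subjects collected 'Unknown".

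Duration is summarised as a continuous variable and in three classes: under 3 months, 3 to under 6 months, and 6 months or more. The same classes split the AE proportions (SAP 8.2.1.3) and, by cross-reference, the improvement rate (SAP 8.2.2), with chi-square or Fisher tests.

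No other rule rescues a partial diagnosis date. SAP section 7 on missing values is marked not applicable, and Appendix 1 also drops ambiguous diagnosis-date entries. By contrast, SAP 8.2.1.2 keeps AEs with partial onset dates and uses the month and year to decide whether they are on-treatment.

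Protocol 7.7.2 gives, as examples of effectiveness subgroups, "demographic and other baseline factors such as sex, age and diagnosis date of MDD".

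**The concern.** A three-class variable with an open top class rarely needs a full date. If a chart gives only the year and that year lies well before the first dose, the subject is in the top class whatever the day and month were. The rule discards that subject anyway, although the SAP uses month and year for AE onset.

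At stake are the duration distribution in the baseline table and the number of subjects in the AE and improvement comparisons by duration. If old diagnoses tend to have vaguer dates, the discarded subjects would come mainly from the top class and the table would understate chronicity.

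**Working it through.** The plan gives no figure on this point, so there is none to reproduce. Two things can be checked: when a partial date still fixes the class, and how far the exclusion could move the results.

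**1. When is the class certain?**

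Inputs: the SAP formula and classes; first doses on each of the 1,097 days from 01 Dec 2015 to 01 Dec 2018 (the data collection dates in Protocol section 4, used as a proxy for first-dose dates). Cut-points of 90 and 180 days are an assumption. The SAP equates 6 months with 180 days only for treatment length ("6 months (180 days) of total administration period of PRISTIQ"), so 91.3 and 182.6 days were also tried.

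Method: take the earliest and latest diagnosis dates compatible with the known part, with the latest capped at the first dose. Put both into the formula. The class is certain if both durations fall in the same class.

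*Only the year known:*

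| Year of diagnosis | First-dose dates for which the class is certain |
|---|---|
| Two or more calendar years earlier | 100%, always 6 months or more |
| Previous calendar year | 563/1,097 = 51% (first doses from about 28 June), always 6 months or more |
| Same year as first dose | 267/1,097 = 24%, always under 3 months |

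For the first row, the worst case is a first dose on 1 January 2016 and a diagnosis on 31 December 2014: 366 + 1 = 367 days.

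*Year and month known, day unknown:*

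| Calendar months before first dose | First-dose dates for which the class is certain |
|---|---|
| 7 or more | 100%, always 6 months or more |
| 0, 1, 2, 4, 5 | 88% to 100% |
| 3, 6 | 5% to 15% |

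For the first row, the worst case is a diagnosis on 31 December 2016 and a first dose on 1 July 2017: 182 + 1 = 183 days. The alternative cut-points change none of the 100% results for long-standing disease; the previous-year figure becomes 50.5%.

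**2. Effect on the reported share**

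Assumptions: N = 600 (the planned enrolment; the analysis sets will be smaller), a true share of 50% with 6 months or more, and d subjects with partial dates.

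- Lower bound, equal loss in both halves: (300 − d/2)/(600 − d) = 50% for any d. No shift.
- Upper bound, all d in the top class: (300 − d)/(600 − d).
  - d = 30 (5%): 270/570 = 47.4%; the class loses 10% of its subjects.
  - d = 60 (10%): 240/540 = 44.4%; it loses 20%.
  - d = 120 (20%): 180/480 = 37.5%; it loses 40%.

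An intermediate case, with a true 60% share and losses of 10% in the top class and 2% below it: 324/(324 + 235.2) = 57.9%.

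**3. Effect on precision**

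Collapse to two groups, with assumed AE rates of 30% (under 6 months) and 20% (6 months or more). Power = Φ[(0.10 − 1.96·se0)/se1], where se0 is the pooled and se1 the unpooled standard error of the difference.

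- 300 v 300: se0 = √(0.25 × 0.75 × 2/300) = 0.03536; se1 = √((0.21 + 0.16)/300) = 0.03512; power = Φ(0.874) = 80.9%.
- 270 v 270 (10% lost from each group): se0 = 0.03727; se1 = 0.03702; power = Φ(0.728) = 76.7%.

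The loss of precision therefore does not depend on differential missingness. These figures treat every partial date as classifiable, so they show the most that the fix could recover.

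**The case against.** **Unknown may mean a wholly unknown date.** The footnote counts subjects recorded as Unknown, and SAP 8.1.2 uses the same expression for disease severity, where it is a complete response. On that reading there is nothing to recover. The exclusion sentence more naturally covers a date with any unknown component, but the SAP should say which it means.

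**Selective loss is not shown.** A reader might infer that the rule mainly removes long-standing cases and so biases the table. The documents do not support this: they give no partial-date rate, overall or by duration. With equal loss the distribution does not move. Nor are recoverable subjects all long-standing, since most recent diagnoses lacking only the day can also be classified.

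**The subgroup factor is not singled out.** A reader might take diagnosis date to be one of three designated factors. Protocol 7.7.2 offers it within an open list of examples, for effectiveness only. Protocol 7.7.3 names gender, age and concurrent disease for safety, and Protocol 7.7 lists four special groups without disease duration.

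**The consequences are small.** SAP 5.1 and 5.2 do not exclude these subjects, so they stay in the overall analyses. The number dropped is footnoted, there is no formal hypothesis, and duration is one of 16 categorised factors. If missingness depends only on duration, AE and improvement rates within each class are not biased.

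**The classes may change.** The SAP says "The above categories can be altered depending on the data distribution", and splitting the top class would make fewer partial dates decisive. A rule applied to whichever classes are finally used still works.

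These objections narrow the point. They give no reason to discard a subject whose class is known.

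**Conclusion.** The point holds as a minor, cheap improvement. On its natural reading, SAP 8.2.1.1 excludes subjects whose duration class is certain, and it treats diagnosis dates more strictly than SAP 8.2.1.2 treats AE onset dates.

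What is established is an avoidable loss of precision wherever such dates occur; how many occur is not documented. Understatement of the share with 6 months or more is conditional on older diagnoses being dated less completely. Under the 50% assumption its size lies between zero and the upper-bound values calculated above. The documents do not support a claim of biased AE or improvement rates within duration classes.

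**What to change.** In SAP 8.2.1.1:

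1. State that only subjects whose duration class cannot be determined are excluded from the categorised analysis.
2. For a partial diagnosis date, compute the shortest and longest compatible durations, with the diagnosis date capped at the first PRISTIQ start. Assign the class when both agree.
3. Define 3 and 6 months in days for this variable.
4. Footnote three counts separately: partial but classified, partial and unclassifiable, and wholly unknown.
5. Keep the continuous summary on complete dates, with its footnoted count. Avoid mid-month or mid-year imputation: with only the year 2017 known and a first dose in March 2017, a mid-year date would fall after treatment began and give a negative duration.

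The cost is a few lines of derivation code and slightly different denominators for the categorical and continuous summaries, which the footnotes explain.

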7.4.5. Administration status for PRISTIQ®

Record the followings with regard to administration status for the study drug. If the posology is changed (including wash-out), please record in a separate row and the reason.

- Treatment start date
- Treatment stop date
- Daily dosage and frequency
- Reason for dose adjustment: Select one among 'planned dose increase or decrease', 'cure or improvement', 'occurrence of adverse event', 'withdrawal due to lack of efficacy' or 'other'. If 'other', record the specific reason.

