7.7. Data Analysis

The data collected in this study will be documented in a Statistical Analysis Plan, which will be maintained by the sponsor. This document may modify the plans outlined in the protocol; however, any major modifications of primary endpoint definitions or their analyses will be reflected in a protocol amendment.

No formal sample size calculations were performed for this study. Six hundred (600 patients) or more will be collected as per the requirement by MFDS. Safety summaries will be based on the safety analysis set defined as those patients who met inclusion / exclusion criteria and completed safety follow-up. Effectiveness summaries will be based on the effectiveness analysis set, defined as those patients who took at least 8 weeks of PRISTIQ® and completed effectiveness evaluation.

In addition, special subject groups -elderly group (more than or equal to 65 years old), hepatic disorder group, renal disorder group and pregnancy group- will be analyzed separately.

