5.2 EFFECTIVENESS ANALYSIS SET

Subject who have been administered PRISTIQ® at least once and evaluated upon its related effectiveness endpoints at least once will be included in the effectiveness analysis set. The effectiveness analysis set is a subset of the safety analysis set.

The following cases are excluded from the effectiveness analysis set:

- Subjects excluded from safety analysis set listed in section 5.1
- Subjects who are assessed as “Unevaluable” on the final effectiveness evaluation on the CRF
- Subjects who administrated PRISTIQ® less than 8 weeks
- Subjects who are assessed on the final effectiveness evaluation before 8 weeks treatment of PRISTIQ®

Statistical analysis on effectiveness parameters will be performed on the effectiveness analysis set.

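### The SAP labels treatment duration a sum of dosing periods but computes a calendar span, so drug-free days count as treatment and the 8-week cut is undefined for interrupted patients

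*SAP*

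**What the plan says.** SAP 8.2.1.1 gives the variable a label: "Total administration period of PRISTIQ® = Sum of each period of administration". For the safety set, and for effectiveness-set patients evaluated after their last dose, it then defines that sum as "Sum of each period of administration = (Last administration end date) – (First administration start date) + 1". For effectiveness-set patients evaluated before the last dose, or still on drug, it uses "Sum of each period of administration = (Date of final effectiveness evaluation) – (First administration start date) + 1".

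The variable feeds the four administration-period categories and the long-term split at 180 days. SAP 8.2.1.3 uses both to break down adverse events, and 8.2.2 uses the same list to break down the improvement rate.

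SAP 5.2 removes from the effectiveness set "Subjects who administrated PRISTIQ® less than 8 weeks". It also removes those evaluated before 8 weeks of treatment. It cites no formula and has no rule on interruptions. SAP 5.3, for the long-term effectiveness set, does have one: "Subjects whose each drug-free period is more than 14 days". Protocol 7.7 describes the effectiveness set as "those patients who took at least 8 weeks of PRISTIQ® and completed effectiveness evaluation".

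Interruptions are captured. Protocol 7.4.5 instructs: "If the posology is changed (including wash-out), please record in a separate row and the reason".

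**The concern.** A sum of dosing periods and a first-to-last span are equal only when there is no gap. For an interrupted patient the SAP gives one variable two values, and a programmer cannot satisfy both lines. The formula is the more explicit of the two, so the likely result is that time off drug is reported as time on drug.

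The plan shows elsewhere that it expects gaps. Total dose is built up interval by interval, the mean daily dose uses a denominator with missed-dose days removed, and 5.3 has a gap exclusion. Only the duration variable and the 8-week set leave gaps unaddressed.

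Two things are at stake. First, the exposure categories and the 180-day split would place some patients in a longer-exposure group than their dosing supports. Second, if the same span is used for the 8-week cut, the improvement rate could include patients who did not take 8 weeks of drug, contrary to Protocol 7.7.

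**Working it through.** **Inputs.** The label and formulas come from SAP 8.2.1.1. The thresholds are 8 weeks = 56 days (SAP 5.2) and 180 days (SAP 5.3 and 8.2.1.1). The category limits are 4, 8 and 12 weeks = 28, 56 and 84 days (SAP 8.2.1.1). Row-level dates come from the CRF (Protocol 7.4.5). The plan states no figure to reproduce. The dosing records below are hypothetical, with day 1 the first dose.

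**Formulas.**
- Span (SAP formula) = last end, or evaluation day, − first start + 1.
- Sum (SAP label) = total over dosing rows of (end − start + 1), cut at the evaluation where that branch applies.

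| Dosing days | Span | Days on drug | Category by span | Category by sum |
|---|---|---|---|---|
| 1-56 | 56 | 56 | 8 to <12 wk | 8 to <12 wk |
| 1-28, 29-56 (dose change only) | 56 | 28 + 28 = 56 | 8 to <12 wk | 8 to <12 wk |
| 1-28, 43-56 | 56 | 28 + 14 = 42 | 8 to <12 wk | 4 to <8 wk |
| 1-14, 43-56 | 56 | 14 + 14 = 28 | 8 to <12 wk | 4 to <8 wk |
| 1-14, 51-60 | 60 − 1 + 1 = 60 | 14 + 10 = 24 | 8 to <12 wk | <4 wk |
| 1-14, 43-90, evaluated day 57 | 57 | 14 + 15 = 29 | 8 to <12 wk | 4 to <8 wk |
| 1-45, 136-180 | 180 | 45 + 45 = 90 | ≥12 wk, long-term | ≥12 wk, not long-term |

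The two definitions agree without a gap, including when a dose change creates a new row. With a gap, the span exceeds days on drug by exactly the length of the gap. In the fifth row, 24 days is 24/56 = 43% of 8 weeks. The last row counts as 180-day use in the safety set, where no gap rule applies.

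**Entry to the 8-week set.** All the interrupted records above reach 56 days by span. By sum, every one except the last falls short. SAP 5.2 does not say which value it uses. The formula in 8.2.1.1 is headed as applying in the effectiveness set, but it sits there as the definition of a baseline characteristic, not as a selection rule. Entry of these patients is therefore possible, not established.

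**Effect on the improvement rate.** If a share f of the set is interrupted and improves at rate p1 against p0 for the rest, the rate moves by f × (p1 − p0). None of these inputs is in the documents. Purely as an illustration, assume f of 2% to 10%, p0 = 80% and p1 of 40% to 60%. The smallest shift is 0.02 × (0.60 − 0.80) = −0.4 points and the largest is 0.10 × (0.40 − 0.80) = −4.0 points. If interrupted patients improve equally often, the shift is zero.

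**Check on a strict remedy.** Final effectiveness is judged at around 8 weeks in patients still on drug (Protocol 7.4.9.2). A patient evaluated on day 56 with one recorded off-drug day has 56 − 1 = 55 summed days, and a hard 56-day summed threshold would drop that patient.

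**The case against.** The span may be deliberate. The SAP's amendment table shows that the duration calculation was revised in versions 2.0 and 3.0, and the missed-dose exclusion for mean daily dose was clarified in version 4.0. That history fits an elapsed-time variable for duration and a net one for dose. On that reading the fault is a wrong label. This is plausible, but the label must then change, and the exposure categories should be described as time since first dose. The mean daily dose itself is not distorted if its missed-dose rule is applied as written.

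The gap of days 15-50 is also extreme. A site that regarded day 14 as the end of treatment would evaluate then, and the fourth exclusion in 5.2 would remove the patient. The 28 days of observation required after an early stop would run to day 42, before the restart on day 51. The case reaches the 8-week set only if a 36-day stop is treated as temporary. This objection stands for long gaps. It has less force for a 14-day gap, where 42 days on drug still count as 56.

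A reader might also take the 5.3 wording literally and conclude that its rule fails, because a patient with one 60-day gap and one 3-day gap does not have every gap over 14 days. That reading is strained. The natural meaning is any single gap over 14 days, so the wording needs tidying but the rule is sound. Alternating 14 days on and 14 off for 180 days would leave 6 × 14 + 12 = 96 days on drug and pass the 5.3 gap rule, but it needs six gaps of exactly 14 days.

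Finally, the study is single-arm with no formal hypotheses, and the effectiveness summaries are mainly descriptive, which limits the consequences.

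**Conclusion.** The contradiction between label and formula in SAP 8.2.1.1 is certain. For any patient with a recorded interruption the stated formula overstates treatment by the length of the gap, and this carries into the administration-period categories and the 180-day long-term category.

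The consequence for the 8-week effectiveness set is conditional. A reader might infer that the improvement rate is known to include patients treated for a fraction of 8 weeks. The documents do not support that, because 5.2 and 5.3 never cite this formula for membership. What they support is that 5.2 leaves its duration unnamed and has no gap rule, so such patients could enter despite Protocol 7.7.

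The number affected cannot be derived from the documents. Any percentage applied to the 600 planned patients would be an assumption, and the wrong base, since the effectiveness set is smaller. The shift of 0.4 to 4.0 points shown above rests wholly on assumed inputs. This should be corrected, but it does not invalidate the study.

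**What to change.** - **SAP 8.2.1.1:** compute total administration period as the sum, over dosing rows with dose above zero, of (end date − start date + 1), cut at the final effectiveness evaluation in the effectiveness set. Use it for the exposure categories and the 180-day split.
- **SAP 5.3:** change the word *each* to *any* in the drug-free-period exclusion.
- **SAP 5.2:** state which duration drives the 8-week cut. Report how many subjects have a drug-free period over 14 days or fewer than 56 summed days. Give the improvement rate with and without them as a sensitivity analysis.

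The summed threshold should not become a hard entry rule for the effectiveness set. As shown, it would drop a patient for a single off-drug day and move a routine-practice population towards uninterrupted completers, which may raise the improvement rate. For the same reason both rates should be shown.

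The cost is SAP wording and a little more programming. The dosing rows are already collected, and no new data or visits are needed.

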8.2.2 Effectiveness Analyses

Statistical analysis on effectiveness parameter after 8 weeks treatment of PRISTIQ® will be done on effectiveness analysis set.

For collected data separately,

- The overall improvement rate (the proportion of patients considered “Improved”) will be estimated with its 95% confidence interval.
- Frequency and percentage of results for Final Effectiveness (‘Improved’, ‘No change’, ‘Worse’) will be summarized.

The improvement rate according to the baseline characteristics listed in section 8.2.1.3 will be analyzed. Chi-square test or Fisher’s exact test will be used for comparing between subcategories of each baseline characteristic

Additionally, the distribution of subjects according to the CGI-I scale (‘1. Very much improved’, ‘2. Much improved’, ‘3. Minimally improved’, ‘4. No change’, ‘5. Minimally worse’, ‘6. Much worse’, ‘7. Very much worse’) at last visit will be summarized.

Following statistical analysis on effectiveness parameter after 6 months(180 days) treatment of PRISTIQ® will be done on long-term effectiveness analysis set.

- Frequency and percentage of results for Final Effectiveness (‘Improved’, ‘No change’, ‘Worse’) will be summarized.
- Distribution of subjects according to the CGI-I scale (‘1. Very much improved’, ‘2. Much improved’, ‘3. Minimally improved’, ‘4. No change’, ‘5. Minimally worse’, ‘6. Much worse’, ‘7. Very much worse’) at last visit will be summarized.

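### The 8-week improvement rate is tested by administration period and long-term use, but in the effectiveness set these factors largely record when the patient was rated

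*SAP*

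**What the plan says.** SAP 8.2.1.1 defines total administration period differently by analysis set.

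- **Safety set.** The period runs from first to last dose. For ongoing treatment: "If the medication is being continued at the completion of the study, last administration end date is replaced with last date collected in data".
- **Effectiveness set, rated after stopping.** "If final effectiveness evaluation is evaluated after last administration end date", the period again runs from first to last dose.
- **Effectiveness set, rated while on drug.** "If final effectiveness evaluation is evaluated before last administration end date or the medication is being continued at the completion of the study", the rule is "Sum of each period of administration = (Date of final effectiveness evaluation) – (First administration start date) + 1".

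SAP 8.2.1.3 lists two factors built on this variable: the period bands, and long-term administration, split at "6 months (180 days) of total administration period of PRISTIQ". SAP 8.2.2, under the analysis after 8 weeks of treatment, states: "The improvement rate according to the baseline characteristics listed in section 8.2.1.3 will be analyzed". The subcategories are compared by chi-square or Fisher's exact test, and SAP 8.1 adds: "All test statistics will be the results of two-sided tests with the statistical significant level of 0.05".

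On timing, SAP 6.2 places the final evaluation at the end of treatment or "at around 8 weeks treatment if PRISTIQ® has been still administered". For long-term use subjects it places it after 6 months. SAP 5.3 lists treatment shorter than 180 days and a final evaluation before 180 days as separate exclusions from the long-term effectiveness set.

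**The concern.** A factor called long-term administration invites the reading that patients treated for 6 months or more are being compared with those treated for less. In the effectiveness set, a patient still on drug when rated is classed by the day of the rating. A p-value in that row would then mix three things: treatment length, time of assessment, and selection of patients who were still being followed and rated late. The same holds for the period bands.

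The label also changes meaning between tables. The adverse event table uses the safety-set period, so one patient can count as long-term there and not in the improvement table.

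**Working it through.** The documents give no figure to reproduce here; 600 patients is a regulatory requirement without a power calculation (Protocol 7.7). The check applies the SAP date rules, counting the first dose as day 1.

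**Step 1: the rule.** Each period is an end date minus the first dose date plus 1, so it equals a day number.

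- Safety set: period = last-dose day, or last data day if ongoing.
- Effectiveness set: period = rating day if the rating precedes the last dose or treatment is ongoing; otherwise last-dose day.

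The effectiveness-set period therefore never exceeds the rating day. Reaching 180 days requires a rating on or after day 180, and reaching 12 weeks requires one on or after day 84.

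**Step 2: example records.**

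| Treatment | Rated | Safety set | Effectiveness set |
|---|---|---|---|
| stopped day 200 | day 56 | 200 (≥180) | 56 (<180) |
| ongoing, last data day 240 | day 56 | 240 (≥180) | 56 (<180) |
| ongoing, last data day 240 | day 182 | 240 (≥180) | 182 (≥180) |
| stopped day 182 | day 190 | 182 (≥180) | 182 (≥180) |
| stopped day 170 | day 182 | 170 (<180) | 170 (<180) |

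The first two rows show the change of class between tables. The last row is the only kind of record in which the 180-day split departs from a split by rating date: last dose before day 180, rating on or after it. That window is narrow if the final evaluation follows the CGI-I timing of within 2 weeks of the last dose.

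**Step 3: the possible practices.**

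- *Week-8 rating used for all.* The ≥180 cell is essentially empty, and long-term users sit in <180.
- *6-month rating used for long-term users (SAP 6.2).* Nobody is misclassed, but ratings at day 180 or later are tested against ratings mostly near day 56, a gap of about 180 − 56 = 124 days or more.
- *Mixture.* Both faults occur. The separate exclusions in SAP 5.3 show that long-term users rated early are foreseen. The SAP does not say which date counts if a patient has two final evaluations.

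**Step 4: cell sizes.** Inputs are the minimum of 60 long-term users (Protocol 7.3.3.1) and 600 patients as an upper bound for the effectiveness set. The share rated only at week 8 is an assumption. The ≥180 cell is 60 × (1 − share).

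| Share rated only at week 8 | ≥180 cell | <180 cell | Long-term users in <180 |
|---|---|---|---|
| 0% | 60 | 540 | 0 |
| 25% | 45 | 555 | 15 (2.7%) |
| 50% | 30 | 570 | 30 (5.3%) |
| 75% | 15 | 585 | 45 (7.7%) |
| 100% | 0 | 600 | 60 (10.0%) |

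**Step 5: what rating date alone could do to the test.** Assume improvement depends only on rating date: p₁ = 70% at week 8, and p₂ = 80% or 85% at 6 months. The two-sided 5% test of two proportions rejects with probability Φ[(|p₂ − p₁| − 1.96·SE₀)/SE₁]. SE₀ uses the pooled rate and SE₁ the separate rates.

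For 540 versus 60 and 70% versus 80%, the pooled rate is 0.71, SE₀ = 0.0618 and SE₁ = 0.0553. Then (0.10 − 0.121)/0.0553 = −0.38, and the probability is 0.35.

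| Cells | 70% vs 80% | 70% vs 85% |
|---|---|---|
| 540 vs 60 | 0.35 | 0.72 |
| 480 vs 120 | 0.60 | 0.94 |

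Treatment length as such has no effect in any of these cases.

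**The case against.** The strongest defence is that the truncation is deliberate and correct. SAP version 3.0 made the calculation specific to the analysis set. A rating on day 60 reflects 60 days of treatment, and doses taken later cannot have produced it. Classing that rating by later continuation would condition on the future. This stands: the truncated period is a sound description of exposure. It does not justify testing it under the label of long-term administration within an 8-week analysis.

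A reader might infer that every long-term user is put in the wrong class, or that up to all 60 are. The documents do not support this as a general statement. SAP 6.2 puts the final evaluation of long-term use subjects after 6 months. Unlike the CGI-I sentence in the same section, it does not say that this rating is additional. Read literally, those still on drug when rated on or after day 180 are classed as ≥180. Saying that all long-term users rated at week 8 are misplaced is true only by construction.

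A reader might also infer that the factors reflect rating dates and nothing else. That is too absolute, because patients rated after stopping keep their true treatment length.

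The comparison is also of limited consequence. SAP section 4 sets no hypotheses, Protocol 7.7.2 makes subgroup comparisons optional, and 6-month results have their own untested analysis. This limits the weight of the point but does not make the two tests interpretable.

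**Conclusion.** The point holds as a flaw in how a defensible variable is used. Among patients on drug at the rating, the two factors are classes of the rating day, and none of the three practices yields a useful test of treatment length. Depending on practice, the ≥180 cell is essentially empty, the test compares assessment times, or both faults occur together.

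The number of patients affected cannot be derived from the documents. The cell sizes rest on assumed shares, and the rejection probabilities of 0.35 to 0.94 rest on assumed improvement rates and cell sizes. They show that the effect could be material, not that it will be. The reach is confined to two exploratory rows of the effectiveness table. The overall improvement rate is not split by these factors and is unaffected. Membership of the long-term effectiveness set and the adverse event comparison are not in question.

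**What to change.** In SAP 8.2.2:

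- Remove the significance tests of the 8-week improvement rate by long-term administration and by total administration period.
- State that this analysis uses the week-8 rating for every subject. Report how many long-term users have only a 6-month final evaluation, and how they are handled.
- Keep the truncated period as a descriptive variable, relabelled as exposure up to the final evaluation, so that it is not confused with the safety-set period in the adverse event table.
- If a long-term contrast is wanted, show week-8 ratings by eventual long-term status, taken from the safety-set period, without a test. Leave 6-month results to the long-term effectiveness set.

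The cost is a wording change and the loss of two exploratory p-values. No new data are needed.
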